**(1) ABSTRACT:**

Significant morbidity, mortality, and related costs are caused by traumatic brain injury (TBI). A simple, effective, and lightweight device worn by athletes or war fighters in the field, designed to mitigate TBI resulting from blast trauma or concussive events, would save lives, and the huge costs incurred for life-treatment of surviving victims. An externally-worn medical device that applies mild jugular compression according to the principle of the Queckenstedt Maneuver (the Device) is being developed by Q30 Sports Science, LLC (Q30). Preliminary research suggests that the Device has the potential to reduce the likelihood of TBI. The currently developed collar (Smith 2009; Smith 2011; Smith 2011; Smith 2012) has been approved for studies in humans and the results indicate safety for use during high demand and maximal exertion activities, *Study ID: 2013-2240, Institutional Review Board - Federalwide Assurance #00002988*). Regarding safety, the externally worn collar is meticulously designed to mimic the body's own omohyoid muscle actions upon the jugular veins that will provide similar pressure and volume increases not to surpass that of a yawn or the mere act of just lying down.

This study will investigate the effectiveness of this device in high school athletes playing a collision sport such as football. The use of helmets during such a high-risk sport will allow for collision measurement devices to be embedded in the helmet and will not affect play or fit of equipment. Athletes participating in this study will be randomly assigned to one of two groups: 1) Device wearing during the season or 2) Non-device wearing during the season. By the nature of the sport selected, it is likely this pilot study will primarily include males, however if any female meets inclusion criteria on the team selected, she will be included in this investigation. The helmets of all participants will be outfitted with an accelerometer which will measure the magnitude of every impact to the head sustained by the athlete. Effectiveness of the device will be determined via differences in longitudinal brain imaging and functional testing following competitive football participation. A subset of athletes who report a diagnosed concussion will also receive additional brain neuroanatomical and neurophysiological testing within a week following the diagnosed concussive event. At each of these time points participants will also undergo various neurocognitive assessments outlined below.

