
E. An *in vivo* clinical trial was approved by CCHMC IRB and was completed in the Cincinnati Children’s Hospital Human Performance Laboratory and Radiology Department (Study ID: 2014-5009; PI: [name]) An *in vivo* clinical trial was performed in hockey players of the proposed intervention device used during sporting competitions to test its effect in ameliorating neuroanatomical and neurophysiological changes to the brain using two widely accepted techniques [diffusion tensor imaging (DTI), and event related potentials (ERPs) utilizing electroencephalography.](Reches 2014) For athletes in the non-intervention group, radial diffusivity (RD, DTI parameter associated with white matter structural integrity(Song 2003; Song 2005)) increased significantly from pre-season to mid-season. By comparison, the athletes in the intervention group did not show a significant change in RD with similar accumulated g-force head impacts. In kind, ERP analysis showed concomitant changes in brain network dynamics in the non-intervention group—the level of change was strongly correlated with the accumulated g-force of the collisions, whereas the intervention group showed no significant change. These group differences indicate that mild jugular vein compression may provide protection from the detrimental effects of collisions and resultant brain injury. These prospective longitudinal data utilized an internal (*in vivo*) approach and demonstrate, for the first time, that it is possible to protect the brain from sports related head impacts.

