**(6) SELECTION & RECRUITMENT OF PARTICIPANTS:**

The purpose of the present study is to generate pilot data for effect size estimation and power analysis for future study. The group size proposed in the aims was determined empirically based on previous neuroimaging studies and study designs reported in the literature. The sample size proposed in this pilot study will not warrant extensive statistical analysis to test the listed hypothesis. This study is expected to lead to an accurate estimate of effect size and variability so that future studies can be designed more rigorously.

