We will recruit up to 60 study participants. The participants (age 14-19 years old) will be recruited from a local school district and local sports clubs and teams. Participants will be recruited using a top-down approach. We have gained the consent and the cooperation of the school district administrations. Presentations and letters from the research team will be given to each participating school to detail the participation requirements and study risks. The high-risk sports which utilize helmets during competition will allow for measurement devices to be embedded in the headgear and will not affect play or fit of equipment. By the nature of the sports selected, it is likely this study will primarily include males, however if any female meets inclusion criteria on the team selected, she will be included in the investigation. Questions regarding participation will be answered during the presentations or through e-mail or phone. Participants will be contacted via telephone to further explain the study, answer any additional questions and to enroll them in the study. The participants and parents/guardians who voluntarily agree to participate will be scheduled to complete the pre-participation testing. The participant and parent/guardian will read and sign the "Consent to Participate in a Research Study" form, approved by the Institutional Review Board of Cincinnati Children's Hospital. If the participant and parent/guardian does not read or sign the form, they will not participate in the study. Once the potential study participants/school teams are identified, they will be allocated to one of two groups: 1) Device wearing during the season or 2) Non-device wearing during the season. This research does not mandate that the participant maintains participation in their sport. The desire to participate in the sporting event is an independent, personal decision separate from the decision to enter into this study. If any athlete chooses to stop participation in the sporting activity then they will also be withdrawn from the study, due to no longer meeting inclusion criteria.

Inclusionary criteria include:

- Normal healthy volunteer
- Able to provide written consent

- Must be 14 years or older and a participant on varsity level high school football team

Exclusionary criteria include:

- Unable to provide written consent
- History of neurological deficits, previous cerebral infarction, or severe head trauma as indicated through pre-season screening:

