### **Injury Surveillance**

*Device and Compliance Acceptance:* The study coordinator will be responsible for providing the appropriate intervention (device or no-device) to each team based on their random

be reported according to criteria outlined in recent multi-investigator consensus documents (McCrary, 2013). The incidence of concussion will be calculated in this study using cases identified through two primary mechanisms: 1) Monitoring of concussion injuries and time missed from planned physical activity by the AT for each team, and 2) weekly inquiries to each coach by the Study Coordinator as to whether any participants are missing time from activity due to concussion. This dual query approach enables the Study Coordinator to cross check the injury and exposure data collected to improve the accuracy of the data. The data secured from the coach regarding each athlete's participation in individual practices and games combined with accelerometer exposure to impacts allows the research team to capture robust individual athlete exposures rather than just combined team exposures.

The athletic trainer will evaluate any athlete for whom a concussive event has been observed (within 24 hours). If criteria for concussive sequelae are not met, the athlete is cleared for return to play. In the event of a positive concussion evaluation by the AT, an MD will perform a second evaluation. Should the MD concur with the AT on a positive evaluation, a diagnosis of isolated concussion is made and the athlete is removed from play and participant is referred for to a post-concussion evaluation. The diagnosing physician will be blinded to the experimental treatment of the study participants.

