**Statistical considerations.** The data analysis will begin with a review of descriptive statistics for all major variables and all major subgroupings of variables in the data set. For the inferential methods, we will use a number of different generalized linear modeling techniques, including linear regression models. All analyses will be conducted using SAS® version 9.3 (SAS Inst, Cary, NC), or Mplus (Muthén, 2007). Initial analyses will be undertaken to inspect data for errors, inconsistencies, and incomplete information. This will include examining the data with simple frequency tables and dot plots for univariate data and scatter plots and multi-way dot plots for bivariate and multivariate data. Data anomalies that cannot be resolved by the Biostatistical/data management team will be sent as queries via email to the project investigator for clarification and/or correction. During the verification process, outlying values will be corrected if necessary. Incomplete information will be corrected and the project investigator will receive updates. To summarize bivariate relationships among predictors and between predictors and outcomes, Chi-square of Fisher's exact test or Spearman's rank correlation coefficient, will be used, as appropriate. For reporting inferential statistics, such as differences in rates or means, 95 percent confidence intervals will be used extensively to quantify degree of clinical efficacy. Unless otherwise stated, statistical tests are considered two-sided and a .05 significance level is used. All models will be adjusted for potential independent predictor variables but will be limited to the number of predictors we can fit in a regression model while maintaining a valid and reliable model. Candidate predictors include amount of playing time, amount of practice time, previous mTBI, weight, age and height. Collinearity will be examined. Linearity assumptions will be checked and transformations examined. In those cases, a log transformation, polynomial terms, or restricted cubic splines will likely be used to relax the assumption of linearity in the regression models. We will remove the nonlinear terms or transformation only if the nonlinear test is non-significant with a  $p \geq .10$ . Additionally, overly-influential observations and distributional assumptions will be checked. Models will be interpreted graphically, predicted values will be examined, and appropriate significance tests will be utilized.

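### No pre-season measure of expected head-impact load is named for the collar versus no-collar models; recording playing role and starter status as a baseline covariate is a cheap gain in precision, of uncertain size

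*Combined protocol and SAP*

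**What the plan says.** **Assignment.** The Abstract has individual athletes randomised: "Athletes participating in this study will be randomly assigned to one of two groups". Section 6 is less definite: "Once the potential study participants/school teams are identified, they will be allocated to one of two groups". Injury Surveillance in section 8 makes the coordinator responsible for "providing the appropriate intervention (device or no-device) to each team based on their random", where the available text breaks off. No legible section describes blocking, stratification, minimisation or matching.

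**Size and aim.** "We will recruit up to 60 study participants". No power calculation is offered: "The group size proposed in the aims was determined empirically based on previous neuroimaging studies and study designs reported in the literature". Section 6 presents the study as a pilot meant to estimate effect size and variability for a later trial.

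**Load and outcome.** Item E of the Summary of Prior Work reports that, in hockey players without the device, the "level of change was strongly correlated with the accumulated g-force of the collisions". That sentence concerns ERP. The device group showed no significant ERP change. For radial diffusivity the item gives only a group contrast at similar load.

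**Models.** Statistical considerations (section 9) says all models will be adjusted, as far as the number of predictors allows: "Candidate predictors include amount of playing time, amount of practice time, previous mTBI, weight, age and height". Statistical analyses then describes an analysis of covariance naming only time and condition, correlations of imaging biomarkers with recorded impacts, and a Poisson model with an exposure offset.

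**The concern.** If impact load drives the change from pre-season to post-season, athletes in high-impact roles will change more than others. Unless something known before assignment captures that, the variation stays in the error term and widens the interval for the effect size that the pilot exists to supply.

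The two listed predictors closest to load do not fill the gap. Playing and practice time are known only once the season has run. A diagnosed concussion removes an athlete from play, and the collar might itself affect participation. Adjusting for a variable that treatment can change does not do the work of a baseline covariate and can alter what the comparison means. Playing role and expected starter status could be recorded before assignment, but the plan names neither.

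**Working it through.** **Plan's own figure.** There is none to reproduce: effect size, SD, power, dropout and allocation ratio are not stated.

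**Benchmark.** Assume 60 athletes, 1:1. The standard error of the group difference is sqrt(2/30) = 0.258 SD, so the 95% half-width is 1.96 x 0.258 = 0.51 SD. The difference detectable with 80% power at two-sided 0.05 is about 0.72 SD.

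**Assumed inputs (not in the documents).** Share of between-athlete load variance explained by role: 0.2, 0.4, 0.6. Correlation of load with the change: 0.4, 0.6, 0.8; the protocol says only that it was strong.

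**Formulas.** If load acts in both arms, R2 = share x correlation^2. If it acts only without the collar, the common slope halves and the variance reduction is R2/4. The standard error is multiplied by sqrt(1 - reduction), and the extra athletes are 60/(1 - reduction) - 60.

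| Share, correlation | Load acts in | Variance reduction | SE cut | Extra athletes |
|---|---|---|---|---|
| 0.2, 0.4 | both arms | 0.2 x 0.16 = 0.032 | 1.6% | 2.0 |
| 0.4, 0.6 | both arms | 0.4 x 0.36 = 0.144 | 7.5% | 10.1 |
| 0.6, 0.8 | both arms | 0.6 x 0.64 = 0.384 | 21.5% | 37.4 |
| 0.2, 0.4 | no-collar arm only | 0.032/4 = 0.008 | 0.4% | 0.5 |
| 0.4, 0.6 | no-collar arm only | 0.144/4 = 0.036 | 1.8% | 2.2 |
| 0.6, 0.8 | no-collar arm only | 0.384/4 = 0.096 | 4.9% | 6.4 |

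At the central value the half-width falls from 0.51 to 0.51 x sqrt(0.856) = 0.47 SD if load acts in both arms, and to 0.51 x sqrt(0.964) = 0.50 SD if it acts in one.

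**Cost of the term.** With simple randomisation, k added degrees of freedom inflate the variance by roughly k/(60 - k - 3): 1/56 = 1.8% for two cells and 3/54 = 5.6% for four. The table is before this cost, so in its weakest rows the net gain is nil or slightly negative.

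**Chance imbalance, if athletes are assigned individually by simple randomisation.** With 30%, 40% or 50% of athletes in high-impact roles, exact enumeration puts the chance of a gap of 20 or more percentage points in role mix at 10%, 13% and 16%. At the central R2 with 40% in such roles, a 20-point gap moves the contrast by 0.2 x sqrt(0.144/0.24) = 0.15 SD, or 0.15/0.258 = 0.6 of a standard error.

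**Balancing or modelling.** A simulation (60 athletes, 6,000 runs per setting) compared stratifying on a median split of a pre-season load proxy with adjusting for the proxy. Standard errors of the group difference, by correlation of proxy with outcome:

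| Setting | Neither | Stratified only | Adjusted only | Both |
|---|---|---|---|---|
| Both arms, 0.35 | 0.257 | 0.244 | 0.244 | 0.244 |
| Both arms, 0.56 | 0.259 | 0.231 | 0.215 | 0.216 |
| No-collar arm only, 0.35 | 0.256 | 0.255 | 0.257 | 0.255 |

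Once the covariate is in the model, balancing adds almost nothing.

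**The case against.** Much of the case against stands.

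- **Unit of assignment.** A reader might infer from the Abstract that athletes are individually randomised without stratification. Section 6 and Injury Surveillance point at least partly to teams, and the latter breaks off where the assignment is being described. Absence of balancing can be asserted only for the legible text. With teams as the unit, blocking within role is unavailable and the imbalance figures above do not apply.
- **The comparator.** The gains are measured against an unadjusted analysis, but the plan says all models will be adjusted, and its list is open. Weight, height, age and previous mTBI are knowable pre-season, and weight and height may track role. The gain beyond them is smaller by an unknown amount. They are only candidates, however, and none is a stated measure of load.
- **The earlier data.** A reader might infer that load is known to drive the outcomes generally. The documents support this for ERP only, only without the device, and with no coefficient. The lower set of figures is therefore a serious possibility.
- **Bias.** A reader might infer that a chance excess of high-impact roles biases the comparison. Under randomisation it does not: the standard error already allows for it, and a shift of 0.6 standard errors is ordinary sampling error.
- **Cost.** The documents mention no roster data, so ready availability is an assumption. A pre-season testing visit does exist, at which the information could be recorded.
- **Pilot status.** Section 6 disclaims extensive hypothesis testing. Because its stated product is an accurate effect size and variability, precision still matters.

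**Conclusion.** The point holds as a cheap, worthwhile improvement. No pre-season measure of expected impact load is named for any collar versus no-collar model, and the load-related predictors that are named arise after assignment. On the assumed inputs, a role covariate is worth about 2 to 37 athletes (10 central) if load acts in both arms, and about 0.5 to 6 (2 central) if it acts only without the collar. Both ranges are before allowing for the other pre-season predictors and for the degrees of freedom spent. They rest on 60 athletes split 1:1 and on correlations that the documents do not give. The documents do not support a claim of systematic bias, nor a claim that stratified allocation is essential.

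**What to change.** 1. Reconcile the Abstract, section 6 and Injury Surveillance on whether athletes or teams are assigned.
2. At the pre-season visit, record playing role group and expected starter status, collapsed to two to four cells.
3. In Statistical considerations and Statistical analyses (section 9), prespecify those cells as a fixed baseline covariate in every collar versus no-collar model, in preference to in-season playing and practice time. The exposure offset in the Poisson rate model is a separate use and is not affected.
4. If athletes are the unit, allocation in small blocks within the cells is an optional addition with little further gain. If teams are the unit, only the covariate applies.

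Cost: one extra item on the pre-season form and one to three model degrees of freedom, which favours few cells. No extra visits or athletes are needed.

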**(2) PURPOSE OF STUDY:**

The purpose of the study is to monitor longitudinal changes in brain structure and function between the preseason and postseason, in a population of football playing athletes wearing the Device and compared to a similar population not wearing the device. Secondly, the purpose is to determine the protection of the device relative to amount and magnitude of sustained head impacts.

**(3) BACKGROUND:**

The Device has the promise of providing a novel mechanism for reducing or preventing the likelihood of TBI, and may be used in conjunction with other protective equipment. TBI is the leading cause of death in individuals under age 45. The cost of TBI in the U.S. is estimated at anywhere from \$50 to \$150 billion, annually. The January, 2008 New England Journal of Medicine reports, “Head and neck injuries, including severe brain trauma, have been reported in one quarter of service members who have been evacuated from Iraq and Afghanistan”(Okie 2005; Xydakis 2005; Hoge 2008). The vast majority of these injuries have resulted from exposure to improvised explosive device (IED) blast waves. Head injuries, concussions and the resulting trauma have been in public discussion recently as the National Football League (NFL) deals with a lawsuit regarding head injuries by about one-third of living former NFL players.

According to NASA, “The oscillation of a fluid caused by an external force, called sloshing, occurs in moving vehicles containing liquid masses, such as trucks, etc.” This oscillation occurs when a vessel is only partially filled. It is hypothesized that the brain faces similar slosh energy absorption during external force impartation.(Turner 2012) Slosh permits external energies to be absorbed by the contents of a partially filled vessel or container by means of inelastic collisions. Tissues of differing densities can decelerate at different rates creating shear and cavitation. If the collisions between objects or molecules are elastic, the transfer of energies to those objects diminishes, minimizing the energies imparted by slosh.(Smith 2012)

Woodpeckers, head ramming sheep and all mammals (including humans) have small, little known and misunderstood muscles in their necks called the omohyoid muscles. Highly G-tolerant creatures of the forest have utilized these muscles to gently restrict outflow of the internal jugular veins thereby “taking up” the excess compliance of the cranial space and ultimately protecting themselves from TBI like tiny “airbags” in a motor vehicle. Rat studies by have demonstrated that we can easily and safely facilitate this muscle’s actions by a well-engineered gentle compression over those muscles.(Smith 2012; Turner 2012)

The medical Queckenstedt Maneuver devised to detect spinal cord compression, gently places pressure over the external jugular veins to increase cerebral spinal volume and pressure. In this maneuver, the veins are compressed while a lumbar puncture monitors the intracranial pressure. “Normally, the pressure rise to the higher ‘plateau’ level occurs instantly upon jugular compression to fall again equally fast upon release of the compression”(Gilland 1969). This incredibly simple principle can be employed to protect soldiers and athletes from TBI by safely, and reversibly, increasing intracranial volume and pressure. The neck collar device is made of Outer collar - hytrel (thermoplastic elastomer),

Inner collar - TPSiV (thermoplastic elastomer), metal insert (stainless steel), and is fitted to the neck provide a comfortable and precise jugular compression that potentially mitigates cerebral slosh (Figure 1).

to

Although the skull, blood, and brain are “almost incompressible,” the vasculature tree of the cerebrum is quite reactive and compressible. As volume is added to the cranium, eventually the compensatory reserve volume is surpassed and the intracranial pressure increases slightly. Increasing cerebral blood volume by just 1-3% safely and reversibly reduces compliance of the cerebral vascular tree and diminishes absorption of slosh energies. Jugular compression increases cerebral blood volume almost instantaneously. As mentioned, this degree of increase has significantly mitigated slosh and TBI in laboratory animals and mimics the highly concussion resistant wild animals that are able to reflexively increase cerebral blood volume through natural jugular compression.

A landmark article, published in the *Journal of Neurosurgery*, used a standard acceleration-deceleration impact laboratory model of mild TBI. The study showed a successful and marked reduction of axonal injury following Internal Jugular Vein (IJV) compression as indicated by immunohistochemical staining of Amyloid Precursor Proteins (APP) (Smith 2012; Turner 2012). It is argued that IJV compression reduces slosh-mediated brain injury by increasing intracranial blood volume and reducing the compliance and potential for brain movement within the confines of the skull. The potential for such technique to mitigate both linear and rotational brain injury in humans by “internal protection” represents the most novel approach to mitigating TBI.

